3.2.2 Secondary

Efficacy will be investigated further using secondary outcomes:

TMD pain days: Percentage of participants with at least a 50% reduction from baseline in monthly TMD pain days. Time Frame: Baseline phase, the 12 weeks of management and until Visit 4.

Definition of TMD pain day: A TMD pain day was any calendar day in which the participant experienced pain, stiffness, soreness, tenderness, in the jaw or temple area or either side being brief or continuous; and/or pain with TMJ biomechanics (chewing, mouth opening or any jaw movement; and/or pain with jaw activities (yawning, kissing, talking); and/or pain with jaw habits (chewing gum, clenching, grinding).

At least a 50% reduction from baseline in monthly TMD days will be determined if the change in monthly TMD days from baseline phase through the 12 weeks treatment phase (3 cycles) * 100 / baseline monthly TMD days less than or equal to -50%.

Functional measures related to TMJ biomechanics and pain related behaviors:

TMD examination and Jaw functional limitation Scale: Change related to TMJ biomechanics/Jaw function and symptomatology in response to TMD examination.

Oral Behaviors (OBC): Changes in parafunctional behaviors

Pressure Pain Thresholds: Changes in myalgia and arthralgia

Graded Chronic Pain Scale (GCPS): Changes in pain intensity and pain related disability

Patient Global Impression of Change (PGIC): Assesses patient perspective of pain improvement

Hospital Anxiety and Depression Scale: Evaluation of Anxiety and depression

Exploratory Endpoint

To investigate the efficacy of Erenumab in decreasing pro-inflammatory cytokine release

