- Graded Chronic Pain Scale (GCPS). The GCPS includes 7 items and assesses 2 dimensions of pain: pain intensity and pain-related disability [40].

- Patient Global Impression of Change (PGIC). This instrument measures change in participant's overall status on a scale ranging from 1 (very much improved) to 7 (very much worse). The PGIC is based on the Clinical Global Impression of Change, which is a validated scale [41, 42].
- Hospital Anxiety and Depression Scale. Evaluates anxiety and depression with a 14-item instrument [43].

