12 STATISTICAL CONSIDERATIONS

12.1 Study Hypotheses

The main objective of the statistical analysis is to estimate change in study endpoints and evaluate the efficacy of Erenumab by testing a priori hypothesis concerning the differences between treatment and placebo.

Erenumab reduces pain and restores function in patients suffering of TMD.

The primary efficacy hypothesis is that Erenumab produces greater change in average pain score (0-100 scale) from Visit 1 to Visit 4 than placebo.

The secondary efficacy hypothesis is that Erenumab produces a greater proportion of patients reaching at least a 50% reduction from baseline in monthly TMD pain days compared to placebo. This will be determined as a change from baseline phase (4 weeks) through the 12 weeks treatment phase (3 cycles) until Visit 4.

Functional measures related to TMJ biomechanics and pain related behaviors:

There is a greater proportion of patients achieving $\geq 30\%$ decrease (score) in limitation of jaw function with the use of erenumab after 12 weeks of treatment compared to placebo.

There is a greater proportion of patients achieving $\geq 30\%$ decrease (score) in oral behaviors with the use of erenumab after 12 weeks of treatment compared to placebo.

There is a greater proportion of patients achieving $\geq 30\%$ increase in value in pressure pain thresholds in temporalis, masseter, trapezius muscles, TMJs and epicondyles with the use of erenumab after 12 weeks of treatment compared to placebo.

There is a greater proportion of patients achieving $\geq 30\%$ decrease in intensity and pain related disability (GCPS) with the use of erenumab after 12 weeks of treatment compared to placebo.

There is a greater proportion of patients achieving $\geq 30\%$ increase in score (impression of improvement/ impression of change/PGIC) with the use of erenumab after 12 weeks of treatment compared to placebo.

There is a greater proportion of patients achieving $\geq 30\%$ decrease (score) in anxiety and depression (change in HADS) with the use of erenumab after 12 Weeks of treatment compared to placebo.

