12.4 Final Analysis Plan

The main goal of the statistical analyses is to estimate change in study primary and secondary endpoints to evaluate efficacy of Erenumab. Intention to treat analysis will be performed using a within-subjects student's pair t-test or repeated measures ANOVA (if more than two time points) to determine significant reduction in pain after drug intervention in each patient. Subsequently, a between-subjects unpaired t-test or two-way mixed designed ANOVA (if more than two time points) will be performed to determine difference between the placebo and erenumab groups. *Post-hoc analysis* will only be conducted following a significant ANOVA test, to protect from Type I errors. We will use a 2-way between subject's repeated measure ANOVA design to determine difference between the Erenumab group and placebo group, or a between-subjects unpaired t-test if two groups only. We will also use student's paired t-test to determine time points of significance. 50% reduction in pain days will be determined as a function of baseline pain days. Where, appropriate similar statistical procedures will be used for secondary endpoints.

Descriptive statistics for safety measures will also be calculated.

We will collect the following data for descriptive purposes and, if necessary, to use as covariates: Demographic information (age and race/ethnicity), rescue medication history, psychological factors and perceived change in overall status (PGIC).

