APPENDIX A: SCHEDULE OF EVENTS

Study Phase	Pre-screening ^A	Screening and Baseline	Randomization and Treatment (12 weeks of treatment/3 cycles of Erenumab)				Follow Up	Early termination
Clinic Visit		V0	V1 ^B	V2	V3	V4	V5	ET
Study Day/	0-4 weeks prior to V0	1-3 weeks prior V1	Day 0	Day 28	Day 56	Day 84	Day 112	
Procedures								
Contact Information	X							
Pre-screening interview Script	X							
Informed consent ^C		X						
Eligibility Review	X	X						
Demographic information		X						
Medical history and Review	X	X	X	X	X	X	X	X
Concomitant medications		X	X	X	X	X	X	X
Concomitant therapies		X	X	X	X	X	X	X
Adverse Event Review			X	X	X	X	X	X
Dispense Daily Symptom Diaries ^D		X	X	X	X	X		
Collect Daily Symptom Diaries ^D			X	X	X	X	X	
Assess compliance with Daily Symptom Diaries			X	X	X	X		
Randomization		X						
Provide study drug injection ^E			X	X	X			

Study Phase	Pre-screening ^A	Screening and Baseline	Randomization and Treatment (12 weeks of treatment/3 cycles of Erenumab)				Follow Up	Early termination
Clinic Visit		V0	V1 ^B	V2	V3	V4	V5	ET
Study Day	0-4 weeks prior to V0	1-3 weeks prior V1	Day 0	Day 30	Day 60	Day 90	Day 120	
Clinical Examination and Tests								
Weight		X	X	X	X	X	X	X
Height		X						
Vital signs		X	X	X	X	X	X	X
Urine pregnancy test		X	X	X	X	X	X	X
TMD Examination		X	X	X	X	X	X	
Pressure Pain Threshold Examination		X	X	X	X	X	X	
Schedule next visit	X	X	X	X	X	X		
Laboratory								
Blood draw for Cytokine release assay		X				X		
Questionnaires								
Symptom Inventory		X	X	X	X	X	X	X
Graded Chronic Pain Scale ^F			X	X	X	X	X	X
Jaw functional Limitation Scale ^F			X	X	X	X	X	X
Oral Behaviors Checklist ^F			X	X	X	X	X	X
Hospital Anxiety and Depression Index ^F			X	X	X	X	X	X

Study Phase	Pre-screening ^A	Screening and Baseline	Randomization and Treatment (12 weeks of treatment/3 cycles of Erenumab/placebo)				Follow Up	Early termination

Clinic Visit		V0	V1 ^B	V2	V3	V4	V5	ET
Study Day	0-4 weeks prior to V0	1-3 weeks prior V1	Day 0	Day 30	Day 60	Day 90	Day 120	
Patient Global Impression of Change ^F			X	X	X	X	X	X

^A Pre-screening can happen by phone or at clinic visit. It may be combined with screening visit and baseline visit (Visit 0).

^B In the case Visit 1 cannot occur after one week of Visit 0, and the participant is to remain in the study; Visit 0 will be repeated as an unscheduled visit. The timing of visits 2-5 and their windows are established from the date of Visit 1.

^C Includes consent to participate in the study and HIPPA

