^D Diary symptom diaries are completed electronically but if a participant opted the paper form, they will be dispensed and collected.

^E The study drug will be administered (S.C.) on Visit 1, Visit 2 and Visit 3.

^F Questionnaires will be completed electronically a day prior to the scheduled visit or distributed on paper format a previous visit to be returned at the scheduled visit.

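### The PGIC responder rule counts a rise of at least 30% as success on a scale where higher means worse; PGIC is also a possible covariate with no visit named

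*Combined protocol and SAP*

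**What the plan says.** Section 3.2.2 makes PGIC a secondary outcome: "Patient Global Impression of Change (PGIC): Assesses patient perspective of pain improvement". Section 8.1 defines its scoring "on a scale ranging from 1 (very much improved) to 7 (very much worse"), so a lower score is a better result. No section describes reverse scoring.

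Section 12.1 sets a responder hypothesis for each functional and behavioural measure. For PGIC, success is at least a 30% "increase in score (impression of improvement/ impression of change/PGIC) with the use of erenumab after 12 weeks of treatment compared to placebo". No reference visit is named.

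Section 12.4 gives no PGIC-specific method. It says only that, where "appropriate similar statistical procedures will be used for secondary endpoints". The same section adds: "We will collect the following data for descriptive purposes and, if necessary, to use as covariates". The list that follows includes "rescue medication history, psychological factors and perceived change in overall status (PGIC"), with no visit and no criterion for when adjustment is needed.

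In Appendix A the row "Patient Global Impression of Change ^F" is marked at Visits 1 to 5 and at early termination, but not at Visit 0. Footnote F says: "Questionnaires will be completed electronically a day prior to the scheduled visit", or on paper handed out at the previous visit. The Visit 1 rating is therefore made before the first injection, and all later scheduled ratings follow at least one dose.

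**The concern.** The scoring in section 8.1 and the success rule in section 12.1 point in opposite directions. A participant whose score rises by 30% has moved towards the worse end of the scale, yet the rule counts that participant as a success for erenumab. The parenthetical gloss in the hypothesis shows that improvement was meant.

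The percentage form is a second fault. PGIC asks the participant how much they have changed. A percentage change in such a rating needs a reference rating, and the only one scheduled before dosing is at Visit 1, when there is no treatment response to rate.

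Applied as written, the responder comparison would penalise an effective drug. If the rule is instead repaired during analysis, its direction, reference and cut-off will have been chosen after data collection, and it is no longer pre-specified.

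The covariate point is separate. PGIC at Visit 2 or later is an outcome of treatment. Adjusting the pain comparison for it would remove part of the effect that the trial sets out to estimate.

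**Working it through.** The plan gives no sample size, power or expected rate for PGIC, so there is no figure to reproduce. The check has three parts.

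**1. Direction of the neighbouring rules in section 12.1**

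| Measure | Better direction | Change counted as success |
|---|---|---|
| Jaw limitation | lower | decrease |
| Oral behaviors | lower | decrease |
| Pressure pain threshold | higher | increase |
| GCPS | lower | decrease |
| HADS | lower | decrease |
| PGIC | lower (section 8.1) | **increase** |

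Only PGIC runs against its own scale.

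**2. Which scores qualify**

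Inputs: integer scores 1 to 7 (section 8.1) and a 30% threshold (section 12.1). For a reference score b, a later score s meets the rule as written if s ≥ 1.3 × b. It would meet a reversed rule if s ≤ 0.7 × b.

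| Reference b | 1.3 × b | Qualifies as written | 0.7 × b | Qualifies if reversed |
|---|---|---|---|---|
| 1 | 1.3 | 2–7 | 0.7 | none |
| 2 | 2.6 | 3–7 | 1.4 | 1 |
| 3 | 3.9 | 4–7 | 2.1 | 1–2 |
| 4 | 5.2 | 6–7 | 2.8 | 1–2 |
| 5 | 6.5 | 7 | 3.5 | 1–3 |
| 6 | 7.8 | none | 4.2 | 1–4 |
| 7 | 9.1 | none | 4.9 | 1–4 |

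- There are 7 × 7 = 49 possible pairs. As written, 6 + 5 + 4 + 2 + 1 = 18 qualify, and in every one s > b.
- The pairs with s < b number 0 + 1 + 2 + 3 + 4 + 5 + 6 = 21. None qualifies.
- From an assumed reference of 4 (the midpoint, taken as no change), only 6 and 7 are successes and a move to 1 is a failure.
- With the direction reversed, a participant starting at 6 or 7 succeeds by reaching the midpoint 4, and one starting at 1 can never succeed. Swapping the one word leaves an unsound rule.

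These are counts of possible pairs, not probabilities. The documents give no PGIC distribution.

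**3. Size of the covariate problem**

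The documents give no correlation between PGIC and pain, so r is assumed. Let pain and PGIC each have unit variance within arm, with PGIC = r × pain + noise, so that treatment acts on PGIC only through pain. A treatment effect d on pain moves PGIC by r × d, and the within-arm slope of pain on PGIC is r. The adjusted effect is

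d − r × (r × d) = d × (1 − r²).

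| Assumed r | Share kept, 1 − r² | Share removed | Estimate from 1,000,000 simulated draws, true d = −0.5 |
|---|---|---|---|
| 0.3 | 0.91 | 9% | −0.451 |
| 0.5 | 0.75 | 25% | −0.376 |
| 0.7 | 0.51 | 49% | −0.256 |

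Dividing the simulated estimates by −0.5 gives 90%, 75% and 51% kept, in line with the formula.

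**The case against.** The best defence is that the intent is plain. The gloss in the hypothesis speaks of improvement, the neighbouring lines use the right direction, and an analyst would probably notice. On that view the realistic result is an undefined rule for one of six supportive measures, not a reversed finding. This limits the likely harm, but it leaves an analyst to settle the rule after the data are in.

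Nor is it certain that the responder rule would drive the PGIC result. Section 12.4 names t-tests and ANOVA and gives no test for proportions, and a comparison of mean scores read against section 8.1 would not be reversed. A separate SAP appears among the supplemental materials and was not available. Both points make the practical effect less certain. Neither changes what section 12.1 says, and the supplemental materials are stated not to be part of the protocol.

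The missing reference visit is not peculiar to PGIC: none of the six lines names one, and Visit 1 is the only candidate for these questionnaires. That is fair. What is peculiar to PGIC is that even a Visit 1 rating is not a sensible baseline for a rating of change.

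On the covariate, use is conditional and no adjusted model is specified, and the other variables in that list also lack a visit. The percentages illustrate a general fact under assumed correlations; they do not measure this plan. That stands, and it is why this is the smaller point.

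**Conclusion.** The concern holds. The PGIC success rule in section 12.1 contradicts the scoring in section 8.1 and is wrong as written. This rests only on the two sections and the absence of any reverse scoring; it needs no outside figure. The percentage form is unsuitable in either direction.

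The reach is limited to one secondary measure, and a comparison of PGIC means would be unaffected. It should be fixed, but it does not threaten the primary endpoint as defined.

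The covariate point also holds, at lower weight. If an on-treatment PGIC rating were used to adjust the pain comparison, the loss would be 9% to 49% of the effect for assumed correlations of 0.3 to 0.7, provided treatment acts on PGIC only through pain.

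**What to change.** In section 12.1, replace the PGIC rule with the proportion of participants in a pre-specified improved category at Visit 4, for example PGIC 1–2, with the cut-off fixed before unblinding. Drop the percentage change; do not merely exchange increase for decrease. State also how a participant without a Visit 4 rating is counted, since Appendix A schedules PGIC at early termination.

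In section 12.4, keep PGIC for description but bar it as a covariate. Restrict any covariates to values measured before the first dose, and keep the other listed variables on that condition.

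The cost is about one sentence in each section, plus the IRB review and approval that section 15.2 requires for any amendment. No new data or visits are needed.

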12.2 Sample Size Considerations

The proposed sample size of 60 randomized patients split into two independent groups is based on a 30-50% reduction in TMD pain scores at follow-up, assuming a power of 90%, alpha = 0.05, assuming a 0.5 (medium) effect size. This was calculated using GPower software. This sample size is also based on the conservative assumption of a 15% patient drop out at follow up.

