4 STUDY DESIGN

60 patients (30 per each arm) aged 18-65 years old of either sex, and any race or ethnicity presenting chronic painful temporomandibular disorders (TMD) will be randomly assigned in a 1:1 parallel, double-blind, phase 2 single center clinical trial, to receive either Erenumab or placebo. Participants will attend 6 clinic visits (Visit 0-Visit 5) over a period of 21 weeks. The study should be completed over a period of 3 years, with an estimated duration of recruitment of 2.5 years.

Participants will be pre-screened in person at the Brotman Facial Pain clinic, the Oral and Maxillofacial Surgery Clinic both at the University of Maryland, School of Dentistry or by telephone. Potentially eligible and interested participants will be scheduled for a Screening and Baseline Visit (Visit 0). During Visit 0, participants will provide informed consent and be evaluated for eligibility; information including demographics, medical history, concomitant medications, and therapies will be collected. In addition, participants will be assessed for pain level, pain symptoms, jaw function, health status, among other measures and a blood sample will be collected. Procedures will include clinical examinations and tests and the dispensation of various questionnaires, all of which are listed in the Schedule of Events (Appendix A).

Participants who show compliance with the Daily Symptom Diary of at least 80% and who meet the pain score (inclusion criteria) for 28 days/4 weeks (baseline period) after Visit 0, will be randomly assigned to one of two groups (Erenumab or placebo) and will be scheduled for Visit 1 within a week of randomization.

At Visit 1, randomized participants will receive the 1st cycle of management and begin a 12-week drug treatment/placebo phase that will be divided into once a month injection/cycle for a total of 3 cycles. During that period, Visits 2-4 will take place, and many of the baseline assessments will be repeated. Between visits, communication will be conducted by telephone. The final study visit, visit 5, will occur 4 weeks after the last assessment (visit 4) and 8 weeks after the last dosage of drug treatment (Visit 3).

The primary endpoint will be the change in a monthly mean pain intensity score derived from the Daily Symptom Diary. Efficacy will be evaluated as the difference between Erenumab arm and the placebo arm in the monthly pain intensity score (on a 0-100 scale) during the 12 week treatment period.

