12.3.2 Efficacy Review

The study's primary aim is to evaluate the effects of Erenumab in reducing pain level and secondary outcomes in participants with chronic TMD. The primary endpoint is change from Visit 0 to Visit 4 in average pain level (0-100) calculated in the month prior to the visit. Secondary outcomes are TMD pain days, jaw function, pain-related disability, and other pain related outcomes.

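### The stated 90% power does not follow from the stated inputs: for the two-sided unpaired between-arm t-test, 60 patients and an effect size of 0.5 give 42–48%

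*Combined protocol and SAP*

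**What the plan says.** Section 12.2 is the only power statement in the document. It concerns "The proposed sample size of 60 randomized patients split into two independent groups" and rests on "assuming a power of 90%, alpha = 0.05, assuming a 0.5 (medium) effect size". It adds: "This sample size is also based on the conservative assumption of a 15% patient drop out at follow up". It refers to a 30–50% reduction in pain scores and to GPower. It does not give the test family, the number of tails, an SD, a placebo response, a number of repeated measures or a correlation.

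The comparison being powered is between arms. Section 12.1 has the primary hypothesis that "Erenumab produces greater change in average pain score (0-100 scale) from Visit 1 to Visit 4 than placebo". Section 12.3.2 says "The primary endpoint is change from Visit 0 to Visit 4 in average pain level (0-100) calculated in the month prior to the visit". The two sections disagree on the starting visit, but both describe a change between two time points. For the between-arm comparison, section 12.4 specifies "a between-subjects unpaired t-test or two-way mixed designed ANOVA (if more than two time points) will be performed to determine difference".

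Other sections describe the endpoint differently. Section 4 speaks of the "difference between Erenumab arm and the placebo arm in the monthly pain intensity score" during the 12 weeks. Section 3.2.1 defines a monthly mean for each cycle and for the follow-up month. The Protocol Summary describes a mean of daily scores over 12 weeks. Section 5.5.2 states that patients withdrawn after randomisation are not replaced.

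**The concern.** A medium standardised effect of 0.5 between two independent groups ordinarily needs far more than 60 patients for 90% power, so the figures in section 12.2 looked incompatible.

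What is at stake is how the result will be read. If the 0.5 is in SD units of the analysed change score, the trial would miss that effect in 52–58% of repetitions (two-sided), not in 10%. Someone relying on the stated 90% could take a non-significant result as evidence that erenumab does not work in TMD, although the data could not rule out the very effect the trial was planned around.

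**Working it through.** **Inputs.** From section 12.2: 60 randomised, two independent groups, power 90%, alpha 0.05, effect size 0.5, dropout 15%. Allocation is 1:1 (section 5.4.1). Evaluable after dropout: 60 × 0.85 = 51, taken as 26 + 25. Two-sided testing is an assumption because tails are not stated; one-sided results are also shown.

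**1. Trying to reproduce the plan's figure with the unpaired t-test.** Power comes from the noncentral t distribution with noncentrality d × √(n₁n₂/(n₁+n₂)) and n₁+n₂−2 degrees of freedom.

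- 30 + 30: 0.5 × √(900/60) = 1.936; two-sided critical value 2.002 (58 df).
- 26 + 25: 0.5 × √(650/51) = 1.785; two-sided critical value 2.010 (49 df).

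| Analysed | Two-sided power | One-sided power |
|---|---|---|
| 30 + 30 | 47.8% | 60.6% |
| 26 + 25 | 41.7% | 54.6% |

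The stated 90% is not reproduced.

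**2. Size needed for 90% at d = 0.5.** Two-sided: 86 per arm, 172 evaluable; 172/0.85 = 202.4, so 203 randomised (204 for equal arms). One-sided: 70 per arm, 140 evaluable; 140/0.85 = 164.7, so 165 (166 for equal arms).

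**3. What 26 + 25 can detect, two-sided.** 90% power for d = 0.93; 80% power for d = 0.80.

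**4. Precision.** The 95% confidence interval half-width is 2.010 × √(1/26 + 1/25) = 0.563 SD. An observed difference of exactly zero would not exclude 0.5 SD.

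**5. Calculations that do land near 60.** None of these settings is stated in section 12.2.

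- Paired within-patient t-test, d = 0.5, two-sided: 44 pairs; 44/0.85 = 51.8, so 52. This tests change from baseline, not erenumab against placebo.
- Within–between interaction, G*Power-style noncentrality λ = f²Nm/(1−ρ), with m time points and correlation ρ, at f = 0.25: 46 evaluable (55 randomised) for m = 2, ρ = 0.5; 50 evaluable (59 randomised) for m = 3, ρ = 0.3. With 51 evaluable and ρ = 0.5, power is 93.8% for m = 2 and higher for more time points.

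An interaction f of 0.25 is not a 0.5 SD difference between arms. With two equal arms, f is half the SD, over time points, of the arm-difference profile in raw-score SD units. A profile's SD is at most half its range, so f = 0.25 needs the arm difference to shift by at least 1.0 SD, whatever m and ρ. For a difference δ that is zero at baseline and constant afterwards, f = δ√(m−1)/(2m). Setting f = 0.25 gives the required δ; setting δ = 0.5 gives the power with 51 evaluable:

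| m | δ needed for f = 0.25 | Power at δ = 0.5, ρ = 0.5 | Power at δ = 0.5, ρ = 0.7 |
|---|---|---|---|
| 2 | 1.00 SD | 41.7% | 61.8% |
| 3 | 1.06 SD | 42.7% | 64.7% |
| 4 | 1.15 SD | 41.3% | 63.9% |
| 5 | 1.25 SD | 39.5% | 62.3% |

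**6. If 0.5 is in raw-score SD units.** Assume equal correlation ρ between all months (the documents give no correlation), use 0.5/√variance as the effective d, and test two-sided with 26 + 25.

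| Analysed quantity | Variance (raw SD² = 1) | Power, ρ = 0.5 | Power, ρ = 0.7 | ρ at which power reaches 90% |
|---|---|---|---|---|
| Month-3 change | 2(1−ρ) | 42% | 62% | 0.85 |
| Month 3, baseline-adjusted | 1−ρ² | 52% | 69% | 0.84 |
| 12-week mean change | (1+2ρ)/3 + 1 − 2ρ | 57% | 79% | 0.78 |
| 12-week mean, baseline-adjusted | (1+2ρ)/3 − ρ² | 77% | 88% | 0.73 |

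**7. The 30–50% reduction.** It is not described as a between-arm difference. Read as one, 0.5 SD equals 0.3 to 0.5 of mean baseline only if the SD is 0.3/0.5 = 60% to 0.5/0.5 = 100% of mean baseline.

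**The case against.** The strongest reply is that the t-test is only one reading. Section 3.2.1 defines a mean for each monthly cycle, section 4 refers to monthly scores, and the Protocol Summary averages over 12 weeks. With more than two time points, section 12.4 leads to the mixed ANOVA, and a G*Power interaction at f = 0.25 can exceed 90% with 51 evaluable. That route is open. But section 12.2 states 0.5, not f = 0.25, and under G*Power's convention that f requires an arm difference of at least 1.0 SD. For a sustained 0.5 SD difference, the same test has 40–65% power at correlations of 0.5–0.7. If this was the calculation, section 12.2 misdescribes the effect it detects.

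A second reply is that 0.5 may be in raw-score SD units, where a high correlation between months raises power. This partly stands. At a correlation of 0.8, the 12-week mean change has 92% power with 51 evaluable. If all 60 are analysed, as an intention-to-treat analysis might achieve, the baseline-adjusted 12-week mean has 92.8% at 0.7. No correlation is documented, however, and baseline pain is not among the possible covariates listed in section 12.4.

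Third, the Supplemental Materials list shows a separately stored SAP, which may hold the G*Power inputs. That is possible, so which calculation was run cannot be settled here, and the paired and interaction settings above are illustrations, not a diagnosis. Finally, this is a single-centre phase II trial and the remedy is wording. That bears on cost, not on whether the stated figure is right.

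**Conclusion.** The concern holds and the statement must be corrected. For the test that section 12.4 names for a two-point change, power at 0.5 is 42–48%, which is 42 to 48 percentage points below the stated 90%. Leaving the number of tails unstated does not rescue it: the one-sided range is 55–61%.

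The result assumes that 0.5 is a standardised difference between arms in the analysed change score, that testing is two-sided, and, for the lower figure, that 51 patients are evaluable. Other readings get to 90% only with an undocumented correlation or with a between-arm effect about twice the one suggested. Confidence in the arithmetic is high. The origin of the 60 remains unknown.

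**What to change.** Keep 60 patients. First retrieve the original G*Power run and put into section 12.2 the test family, tails, effect-size index, number of measures and correlation, together with the between-arm difference which that test detects. If the separately stored SAP holds these settings, copy them across.

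If the run was the unpaired t-test, replace the power statement with wording such as:

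> Sixty randomised patients, about 51 evaluable after 15% loss, give 90% power for a between-arm standardised difference of 0.93 (80% for 0.80) with a two-sided unpaired t-test at alpha 0.05. Power for a difference of 0.5 is about 42%.

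Replace the 30–50% reduction with a between-arm difference in points on the 0–100 scale and the SD assumed for it. Add that a non-significant primary result will be interpreted from the confidence interval for the arm difference and not taken as evidence of no effect.

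The cost is protocol wording and one check of the original calculation. The stated power becomes less favourable. No patients are added and the planned analysis does not change.
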